### 2.2 RISK/BENEFIT ASSESSMENT

#### 2.2.1 KNOWN POTENTIAL RISKS

Potential risks associated with this proposed study are expected to be minimal. No experimental pharmacological intervention or invasive medical device intervention will be used in the study.

### Haptic Module & Insole Device

The developed system consists of the sensing insole and the electronics enclosure. The insole slides into the subject's shoe, underneath their existing shoe insole (if removable) and connects to the electronics enclosure through a physical cable. The electronics enclosure clips onto the exterior side of the subject's shoe. The system will be designed to minimize volume (e.g., the insole is <1mm thick) and avoid any hard components in the shoe. Similar systems have been tested by Innovative Design Labs (e.g., RxFunction Walkasins and PhySens-IMM) and found to be a non-significant risk device. The Haptic Module wraps around the lower leg and can be worn on top of the clothing for comfort.

Potential risks of wearing the haptic module and insole device include:

- Foot/ankle pain or discomfort
- Skin irritation or wounds
- Falls

### Assessments/Interview

Participants will be asked to complete the NFOG-Q, CFOG-Q, and the Falls Questionnaire. They will also be asked to complete a structured interview with questions about their experience with using the device within their home and community. Completing the questionnaire and answering the structured interview questions may be difficult or tiring for participants and/or may result in emotional side effects.

### Loss of Confidentiality

There may be a slight possibility of breach of confidential information that was collected. However, the following procedures will be implemented to reduce this risk:

- Data collection and reporting tools will be developed and stored internally.
- Data collected and stored electronically will remain confidential and secure (e.g., secured server and password protected files [Research Electronic Data Capture; REDCap]).
- Study binders will be stored in a locked file cabinet within a locked office.
- After the study is closed, all subject identifiers will be destroyed.

## 2.2.2 KNOWN POTENTIAL BENEFITS

There are no known potential benefits to participants in this study. This study may help other people with PD in the future who have problems with walking and FOG.

## 2.2.3 ASSESSMENT OF POTENTIAL RISKS AND BENEFITS

We believe the potential risks to the participants in this study are minimal and that the benefit of testing the haptic module and insole device outweighs the potential risks.

## 3 OBJECTIVES AND ENDPOINTS

OBJECTIVES	ENDPOINTS
Primary	
Aim 3 : To validate the haptic module and insole device system and evaluate its efficacy with an in-community clinical trial.	Duration of FOG events.

## 4 STUDY DESIGN

### 4.1 OVERALL DESIGN

Study Design:

This study is an unblinded, uncontrolled, unrandomized, 1-arm clinical trial.

Hypotheses:

We hypothesize that easy to use, accurate, exogenous cueing in response to FOG events will decrease duration these events.

Randomization:

N/A

Study Intervention:

Participants will be provided a haptic module and insole device to use within their home and community for 5 weeks. Additional details of the intervention are discussed in **Section 6.1**.

### 4.2 SCIENTIFIC RATIONALE FOR STUDY DESIGN

Justification for an unblinded study: This is a Phase II study. All participants will receive the intervention; therefore, participants and study staff will not be blinded.

Justification for an uncontrolled/unrandomized study: This is a Phase II study. All participants will receive the intervention; therefore, there will be no control group and no randomization.

### 4.3 JUSTIFICATION FOR INTERVENTION

The Phase I effort successfully created a prototype insole, tested its robustness, and created an algorithm to detect FOG events (sensitivity 80%, specificity 92%). The proposed Phase II effort will transition the prototype insole into a production ready state, augment it with a charging mat and external cuing device, and evaluate the efficacy of the system with in-lab and in-community clinical trials.

### 4.4 END-OF-STUDY DEFINITION

A participant is considered to have completed the study if he or she has completed study/treatment visits and assessments. Study withdrawals are described in **Section 7**. The end of the study is defined as completion of the post-treatment visit shown in the Schedule of Activities, **Section 1.3**.

## 5 STUDY POPULATION

### 5.1 INCLUSION CRITERIA

In order to be eligible to participate in this study, an individual must meet all of the following criteria:

- Ability to provide and provision of signed and dated informed consent form.

- Age 45 or older
- Diagnosis of idiopathic PD, as determined by a movement disorders neurologist in accordance with the PD Society Brain Bank diagnostic criteria.
- Evidence of presence of freezing gait as a symptom. Determined from combination of clinical examination (observation of freezing) and NFOG-Q.
- Able to complete a 2-minute walk test at the pre-treatment visit.
- Currently on a stable prescription medication regimen for PD and willing to adhere to the regimen during the study.
- Ability to don and doff the insole and haptic module independently or have daily assistance during the study intervention.

## 5.2 EXCLUSION CRITERIA

An individual who meets any of the following criteria will be excluded from participation in this study:

- Non-English speaking
- History of musculoskeletal disorders that significantly affect movement of lower limbs as determined at the time of enrollment.
- Other significant neurological disorders that may affect participation or performance in the study.
- Neuropathy at the ankle assessed at the pre-treatment visit using the haptic module.
- Hallucinations
- Non-ambulatory
- Legally Blind
- Symptomatic hypotension
- Any condition which would limit sensation in the legs or requires use of wraps, bandages or other items which may limit sensation in the legs (e.g., lymphedema) that would interfere with the performance of the haptic device, in the opinion of the Investigator

## 5.3 LIFESTYLE CONSIDERATIONS

N/A

## 5.4 SCREEN FAILURES

### **Pre-screening Phone Call:**

All potential participants will undergo a pre-screening phone call to determine whether they meet the inclusion/exclusion criteria. Participants will be considered ineligible if they do not meet one or more of the inclusion criteria or meet one or more of the exclusion criteria during pre-screening. We will collect information on why participants are ineligible or decide not to move forward with the trial.

### **Pre-treatment Visit:**

Screen failures are defined as participants who are considered eligible during the pre-screening phone call, but it was subsequently determined that they do not meet one or more of the inclusion criteria or meet one or more of the exclusion criteria at or after the Pre-treatment visit. We will collect information on why participants screen fail or decide not to move forward with the trial.

### **Rescreening:**

Individuals who do not meet the criteria for participation in this trial (ineligible or screen failure) because of meeting an exclusion criteria that is likely to change over time (e.g., symptomatic hypotension) may be rescreened up to one time.

## 5.5 STRATEGIES FOR RECRUITMENT AND RETENTION

**Recruitment:** Individuals with PD will be recruited by clinician referrals from Struthers Parkinson's Center, HealthPartners Neuroscience Center, and other HealthPartners and Park Nicollet clinics. We will also advertise our research study by distributing flyers to physicians and throughout the clinics. Recruitment flyers will also be provided to community organizations, for example, Parkinson's Foundation and American Parkinson Disease Association. If we encounter difficulties with recruitment, we plan to submit an amendment to the IRB to contact HealthPartners patients and members and invite them to participate. To reach our target enrollment, we anticipate that we will need to screen 75 people, and of those 36 individuals will sign the informed consent.

**Remuneration:** Participants will be provided a gift card totaling \$150 per participant at the post-treatment visit for completing the study (end of study). If participants choose to withdraw from the study early and complete the early withdrawal visit, they will receive a gift card payment of \$75. For individuals traveling a long distance ( $\geq 50$  miles each way), we can also reimburse for travel costs at a mileage rate of \$0.67 per mile.

## 6 STUDY INTERVENTION(S) OR EXPERIMENTAL MANIPULATION(S)

### 6.1 STUDY INTERVENTION(S) OR EXPERIMENTAL MANIPULATION(S) ADMINISTRATION

#### 6.1.1 STUDY INTERVENTION OR EXPERIMENTAL MANIPULATION DESCRIPTION

The study intervention for all participants is the use of the haptic module and insole device within their home and community for 5 weeks. Participants will be asked to wear the devices as much as possible during the 5-week period. For example, whenever they don their shoes to walk around within their home or the community, they will also wear the devices. Participants will receive the system with cueing disabled. Cueing will be enabled at the end of week 1 and disabled at the end of week 4 automatically via the cellular base station provided to participants. If any issues occur with the remote enabling and disabling of the cueing devices, participants will be instructed to stop wearing the devices during weeks 1 & 5.

#### 6.1.2 ADMINISTRATION AND/OR DOSING

The main purpose of this study is to establish the robustness and efficacy of the haptic module and insole device through long-term, continuous use while subjects proceed with their activities of daily living at home and in the community. Data will be collected in three parts. Part 1 will collect data for 7 days with the cueing intervention turned off to establish a baseline. Part 2 will collect data over 21 days with the cueing intervention turned on. Part 3 will examine the wash-out effects of cueing by collecting for an additional 7 days with the cueing intervention turned off. Throughout this trial, daily dairies of FOG episodes, user impressions, and adverse events will be collected. Data from the insole will automatically (no participant interaction for the duration of the study) be downloaded by the charging mat's nRF52840

BLE radio/processor and stored to a secure digital card. Participants will be contacted weekly by the research coordinator to discuss use of the device and compliance with protocol.

The sensing device consists of two parts for each leg: the Haptic Module and the Insole (Figure 1). The Haptic Module wraps around the lower leg (Figure 2) of the user and contains electronics for wireless communication, a microprocessor, and four vibrating motors that provide gentle tactile sensory cues to the front, back, medial, and lateral surfaces of the user's leg when a FOG event is detected. The Haptic Module has a power button, two status LEDs, and a reset button. Power is supplied by a rechargeable internal battery.

The Insole is a pressure-sensitive insert that fits in a regular shoe with a battery and electronics for sampling pressure measurements. The electronics are housed in a sealed plastic case that securely clips to the outside of the wearer's shoe (Figure 2). The insole has a single status light and no buttons. Users recharge the insole and haptics module via USB connectors.

Both the Haptics Module and Insole contain a PhySens™ Intelligent Motion Module (PhySens-IMM), Innovative Design Lab's (IDL) compact motion sensing and processing platform. The PhySens-IMM is designed to sense motion information using its onboard MEMS accelerometer, gyroscopes, magnetometers, and barometer and to process this information in real time using its onboard processors. Results are wirelessly transmitted via Bluetooth Low Energy (BLEv5) and stored on a local micro-SD card. Uses for the PhySens-IMM range from exercise recognition to camera orientation estimation to wheelchair performance monitoring. This device is part of the PhySens™ ecosystem that includes a variety of sensor types designed to monitor important aspects of daily life such as sleep, exercise, cognitive state, gait, etc. The data obtained from the PhySens-IMM is used to detect FOG events.

In previous studies, IRBs have determined that Walkasins meet the regulatory definition of a non-significant risk device because they do not meet the definition of a significant risk device. The device to be used in this study is based on the commercially available Walkisons device with the insole to haptics cable removed and integration of the PhySens-IMM.

## 6.2 FIDELITY

### 6.2.1 INTERVENTIONIST TRAINING AND TRACKING

**Training:**

HealthPartners/Park Nicollet research staff will be trained by Innovation Design Labs, Inc. staff on how to use the haptic module and insole device.

**Tracking:**

All training sessions will be documented on a training log. This will include dates and times of the trainings and the names and signatures of those involved.

**6.3 MEASURES TO MINIMIZE BIAS: RANDOMIZATION AND BLINDING**

N/A

**6.4 STUDY INTERVENTION/EXPERIMENTAL MANIPULATION ADHERENCE**

Participants will be asked to adhere to study visits and to complete study assessments. Participants will remain active unless withdrawn from the study (see **Section 7**). We will track participants' adherence to the intervention, as well as completion of the assessments. These will be documented in the relevant electronic case report forms (eCRF).

**6.5 CONCOMITANT THERAPY**

N/A

**6.5.1 RESCUE THERAPY**

N/A

**7 STUDY INTERVENTION/EXPERIMENTAL MANIPULATION DISCONTINUATION AND PARTICIPANT DISCONTINUATION/WITHDRAWAL****7.1 DISCONTINUATION OF STUDY INTERVENTION/EXPERIMENTAL MANIPULATION**

When a participant who signed the consent form chooses to discontinue participation in the study or study intervention, or if the principal investigator (PI) and co-investigators determine that a participant should discontinue participation, they will be withdrawn from the study. A withdrawal will either be defined as 'Participant Withdrawal' or 'PI Withdrawal'. The participant will be asked to complete an early withdrawal phone call within 14 days from the date the intervention was discontinued. The purpose of the phone call will be to record any adverse events (AEs) or serious adverse events (SAEs) that may have occurred after the discontinuation of treatment. Research staff will attempt to call the participant up to 3 times.

The data that will be collected at the time of study withdrawal will include the following:

- The reason(s) for discontinuation of the study intervention.

The data that will be collected during the early withdrawal phone call will include the following:

- AEs or SAEs that occurred since the time of withdrawal.

## 7.2 PARTICIPANT DISCONTINUATION/WITHDRAWAL FROM THE STUDY

Participants are free to withdraw from participation in the study at any time upon request. An investigator may discontinue a participant from the study for the following reasons:

1. Significant study visit or intervention non-compliance.
2. Lost-to-follow up; unable to contact subject (see **Section 7.3, Lost to Follow-Up**)
3. Any event or medical condition or situation occurs such that continued collection of follow-up study data would not be in the best interest of the participant or might require an additional treatment that would confound the interpretation of the study.
4. The participant meets an exclusion criterion (either newly developed or not previously recognized) that precludes further study participation.

The reason for participant discontinuation or withdrawal from the study will be recorded on the relevant eCRF.

## 7.3 LOST TO FOLLOW-UP

A participant will be considered lost to follow-up if he or she fails to attend any scheduled study visit and study staff are unable to contact the participant after at least 3 attempts.

The following actions must be taken if a participant fails to attend any required study visit:

- Study staff will attempt to contact the participant, reschedule the missed visit, counsel the participant on the importance of maintaining the assigned visit schedule, and ascertain if the participant wishes to and/or should continue in the study.
- Before a participant is deemed lost to follow-up, the investigator or designee will make every effort to regain contact with the participant (where possible, telephone calls or e-mail – if no answer leave a voicemail on the first and last attempt). These contact attempts will be documented.
- Should the participant continue to be unreachable, he or she will be considered to have withdrawn from the study with a primary reason of lost to follow-up.

# 8 STUDY ASSESSMENTS AND PROCEDURES

## 8.1 ENDPOINT AND OTHER NON-SAFETY ASSESSMENTS

**Demographics:** Demographic information will be collected, including gender, age, race, ethnicity, height, weight, marital status, and employment status.

**Protected health information collected:** Name, medical record number, birth date, phone number, address, email address, and medical history, including date of PD diagnosis.

**New Freezing of Gait Questionnaire (NFOG-Q):** The NFOG-Q is a self-report questionnaire with 9 items that measure FOG.

**Characterizing Freezing of Gait Questionnaire (C-FOGQ):** The C-FOGQ is a self-report questionnaire that provides insights into the triggers of freezing.

**Falls Questionnaire:** The falls questionnaire is a 4-item self-report survey including questions about any recent falls. The questionnaire was developed by the [name] at the University of Minnesota.

**FOG Diary:** Participants will be provided paper diaries to keep track of their FOG events and will be asked to report the information during the weekly phone call for the 5-week intervention.

**Adherence:** The participant's adherence to using the haptic module and insole device will be measured. Daily use of the device will be recorded during the weekly phone call for the 5-week intervention.

**Structured Interview:** Participants will be asked to complete a structured questionnaire at the post-treatment visit. The interview will include questions about their experience with using the device within their home and community.

## 8.2 SAFETY ASSESSMENTS

### **Assessment of Adverse and Serious Adverse Events:**

AEs and SAEs will be monitored by research staff throughout the study. Research staff will immediately notify the PI and utilize the eCRF to record and categorize any AEs or SAEs. The PI will review all AEs or SAEs and report them accordingly, as discussed below.

## 8.3 ADVERSE EVENTS AND SERIOUS ADVERSE EVENTS

### 8.3.1 DEFINITION OF ADVERSE EVENTS

This protocol uses the definition of AE from 21 CFR 312.32 (a): any untoward medical occurrence associated with the use of an intervention in humans, whether or not considered intervention related.

### 8.3.2 DEFINITION OF SERIOUS ADVERSE EVENTS

This protocol uses the definition of SAE from 21 CFR 312.32 (a): An AE or suspected adverse reaction is considered "serious" if, in the view of either the investigator or study clinician, it results in any of the following outcomes: Death, a life-threatening AE, inpatient hospitalization or prolongation of existing hospitalization, a persistent or significant incapacity or substantial disruption of the ability to conduct normal life functions, or a congenital anomaly/birth defect. Important medical events that may not result in death, be life-threatening, or require hospitalization may be considered serious when, based upon appropriate medical judgment, they may jeopardize the patient or subject and may require medical or surgical intervention to prevent one of the outcomes listed in this definition.

### 8.3.3 CLASSIFICATION OF AN ADVERSE EVENT

#### 8.3.3.1 SEVERITY OF EVENT

For AEs not included in the protocol defined grading system, the following guidelines will be used to describe severity.

1. **Mild** – Events require minimal or no treatment and do not interfere with the participant's daily activities.
2. **Moderate** – Events result in a low level of inconvenience or concern with the therapeutic measures. Moderate events may cause some interference with functioning.
3. **Severe** – Events interrupt a participant's usual daily activity and may require systemic drug therapy or other treatment. Severe events are usually potentially life-threatening or incapacitating. Of note, the term "severe" does not necessarily equate to "serious".

---

#### 8.3.3.2 RELATIONSHIP TO STUDY INTERVENTION/EXPERIMENTAL MANIPULATION

All AEs will have their relationship to study procedures, including the intervention, assessed by an appropriately trained clinician based on temporal relationship and his/her clinical judgment. The degree of certainty about causality will be graded using the categories below.

- **Definitely Related** – There is clear evidence to suggest a causal relationship, and other possible contributing factors can be ruled out. The clinical event, including an abnormal laboratory test result, occurs in a plausible time relationship to study procedures administration and cannot be explained by concurrent disease or other drugs or chemicals. The response to withdrawal of the study procedures should be clinically plausible. The event must be pharmacologically or phenomenologically definitive.
- **Probably Related** – There is evidence to suggest a causal relationship, and the influence of other factors is unlikely. The clinical event, including an abnormal laboratory test result, occurs within a reasonable time after administration of the study procedures, is unlikely to be attributed to concurrent disease or other drugs or chemicals, and follows a clinically reasonable response on withdrawal.
- **Potentially Related** – There is some evidence to suggest a causal relationship (e.g., the event occurred within a reasonable time after administration of study procedures). However, other factors may have contributed to the event (e.g., the participant's clinical condition, other concomitant events). Although an AE may rate only as "possibly related" soon after discovery, it can be flagged as requiring more information and later be upgraded to "probably related" or "definitely related", as appropriate.
- **Unlikely to be related** – A clinical event, including an abnormal laboratory test result, whose temporal relationship to study procedures administration makes a causal relationship improbable (e.g., the event did not occur within a reasonable time after administration of the study procedures) and in which other drugs or chemicals or underlying disease provides plausible explanations (e.g., the participant's clinical condition, other concomitant treatments).
- **Not Related** – The AE is completely independent of study procedures administration, and/or evidence exists that the event is definitely related to another etiology. There must be an alternative, definitive etiology documented by the clinician.

---

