#### 8.3.4 TIME PERIOD AND FREQUENCY FOR EVENT ASSESSMENT AND FOLLOW-UP

The occurrence of an AE or SAE may come to the attention of study personnel during study visits and interviews of a study participant.

All AEs, not otherwise precluded per the protocol, will be captured on the appropriate eCRF. Information to be collected includes event description, time of onset, clinician's assessment of severity, relationship to study procedures (assessed only by those with the training and authority to make a diagnosis), and time of resolution/stabilization of the event. All AEs occurring while on study will be documented appropriately regardless of relationship. All AEs will be followed to adequate resolution.

Any medical or psychiatric condition that is present at the time that the participant is screened will be considered as baseline and not reported as an AE. However, if the study participant's condition deteriorates at any time during the study, it will be recorded as an AE.

Changes in the severity of an AE will be documented to allow an assessment of the duration of the event at each level of severity to be performed. Documentation of onset and duration of each episode will be maintained for AEs characterized as intermittent.

Study staff will record events with start dates occurring any time after study enrollment until study completion. At each in-person visit or phone call, study staff will inquire about the occurrence of AE/SAEs since the last inquiry. All reported events will be monitored until resolution or study completion. Any reported event that is definitely or probably related to the intervention will be followed until resolution or stabilization.

---

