#### 9.4.4 SAFETY ANALYSES

AE/SAEs will be reported as described in section 8.3 of this document. They will be classified by severity, relationship to study procedures, and expectedness. No other formal safety analyses will be conducted.

---

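### The causality scale in Section 8.3.3.2 will tend to place isolated falls at a cue in Potentially Related whether or not the cue contributed, and the named AE items do not record device wear or cue status at onset

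*Combined protocol and SAP*

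**What the plan says.** Section 8.3.3.2 has a trained clinician grade each event's relationship to the study procedures, including the intervention, from timing and clinical judgment. There are five grades:

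- Definitely Related needs an event that "cannot be explained by concurrent disease or other drugs or chemicals", with other contributors ruled out and a plausible response to withdrawal.
- Probably Related needs one that "is unlikely to be attributed to concurrent disease or other drugs or chemicals, and follows a clinically reasonable response on withdrawal".
- Potentially Related needs some evidence of causality. It then adds: "However, other factors may have contributed to the event (e.g., the participant's clinical condition, other concomitant events". It may be upgraded when more information arrives.
- Unlikely to be related and Not Related cover implausible timing with another explanation, and a documented alternative cause.

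Section 6.1.2 says the motors deliver the cue "when a FOG event is detected". Section 5.1 requires evidence of freezing for entry. Section 2.2.1 introduces its device risks with "Potential risks of wearing the haptic module and insole device include", and falls are on that list.

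On data capture, Section 8.3.4 states: "Information to be collected includes event description, time of onset, clinician's assessment of severity, relationship to study procedures", and also time of resolution. On analysis, Section 9.4.4 says of adverse events: "They will be classified by severity, relationship to study procedures, and expectedness". It plans no other formal safety analysis.

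**The concern.** The upper grades ask two things that suit a drug reaction better than a fall: that the underlying disease is an improbable cause, and that the event responds when exposure is withdrawn. Here the exposure is triggered by a sign of the disease, and a single fall is over at once. Two falls at a cue, one caused by freezing alone and one to which the cue contributed, look the same on these criteria.

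Relationship is one of only three classifications in the planned safety analysis, so a low count of definite or probable falls could be read as reassurance about the device when it partly reflects the scale. Other sources of fall data are thin: Section 8.3.8 names no events of special interest, and the schedule in Section 1.3 gives the Falls Questionnaire only before treatment. The grade may also affect follow-up, because one sentence of Section 8.3.4 singles out definitely or probably related events for follow-up to resolution or stabilization.

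**Working it through.** The plan states no figure on this point, so the main check sets the criteria against the kinds of fall that can occur.

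| Fall | Disease criterion for Probably | Withdrawal criterion | Likely grade |
|---|---|---|---|
| Device off the leg | Not met | Not met | Unlikely or Not Related, if non-wear is known |
| Isolated, at a cue in a true freeze, cue did not contribute | Hard to meet | Nothing to observe | Potentially Related |
| Isolated, at a cue in a true freeze, cue contributed | Hard to meet | Nothing to observe | Potentially Related |
| Isolated, at a cue fired outside a freeze | Can be met | Nothing to observe | Potentially Related on a literal reading; judgment may go higher |
| Repeated in cued weeks, ceasing in week 5 | Open to judgment | Can be met | Probably Related is reachable |

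The second and third rows are the problem: the grade does not distinguish them. The first and fourth rows can be recognised only if wear and cue status at onset are known.

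**How often a cue fires outside a freeze.** Section 4.3 gives Phase I sensitivity 0.80 and specificity 0.92. Let p be the share of assessed walking windows that are true freezes. The documents do not give p, and treating the two accuracy figures as per-window rates is also an assumption.

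Share of cues outside a freeze = 0.08(1 − p) / [0.80p + 0.08(1 − p)]

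- p = 1%: 0.0792 / (0.0080 + 0.0792) = 91%
- p = 5%: 0.0760 / (0.0400 + 0.0760) = 66%
- p = 10%: 0.0720 / (0.0800 + 0.0720) = 47%
- p = 20%: 0.0640 / (0.1600 + 0.0640) = 29%
- p = 50%: 0.0400 / (0.4000 + 0.0400) = 9%

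So the overlap of cue and freeze is not complete, and how far it falls short is unknown.

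**Exposure.** Section 6.1.2 has cueing off for 7 days, on for 21 and off for 7. Cue-on time is 21/35 = 60% and cue-off time 14/35 = 40%. With 36 participants that is 36 × 21 = 756 and 36 × 14 = 504 participant-days; with the 29 required by Section 9.2 it is 609 and 406. With equal wear and no cue effect, about 60% of falls would be expected in the cue-on period. That benchmark does not depend on the causality grade.

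**Events to be graded.** Cued time is 36 × 3 = 108 person-weeks, or 29 × 3 = 87 after attrition. At an assumed 0.1 to 0.5 falls per person-week, that is about 11 to 54 falls, or about 9 to 44. These are falls of every kind in cued weeks, not a count of misgraded falls.

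**The case against.** A reader might infer that the scale yields almost no device-attributed falls by construction, or that it gives every fall the same grade. The documents do not support either reading:

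- Potentially Related is itself a related grade, and Section 9.4.4 sets no cut at Probably.
- A fall with the device off fits the two lowest grades.
- Disease must be ruled out only for Definitely; Probably asks that it be unlikely.
- Specificity of 92% means some cues fire outside a freeze.
- The off-on-off design can show a withdrawal response for repeated falls.
- The grade rests on clinical judgment and can be raised later.

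The data gap is also partial. Onset time places a fall in a cue-on or cue-off week, Section 8.1 records daily device use, Section 6.1.2 has daily diaries covering adverse events, and the list in Section 8.3.4 need not be exhaustive. Serious events go to the IRB whatever their grade, and the data safety officer reviews trends.

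All of this stands, and it limits the point. It does not remove it. Daily use does not show whether the device was worn, or a cue felt, at the moment of a fall. Upgrading depends on further information that no named AE item supplies. The unanticipated-problem route in Section 8.4.1 accepts possibly related events but also requires them to be unexpected, and falls are a listed risk.

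**Conclusion.** The point holds for isolated falls at a cue during a true freeze. These will tend to be graded Potentially Related regardless of the cue's contribution, so few falls will reach the top two grades, and the named AE items do not help separate the cases. The absence of definite or probable falls would be weak evidence that the cue is safe.

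The size cannot be stated: the documents give neither a fall rate nor the share of cues that coincide with a freeze, and the figures above rest on assumed values of both. The conclusion rests on the category conditions being applied as written. It is a correctable weakness in attribution and reporting, worth fixing because the circumstances of a fall are hard to recover afterwards.

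**What to change.** 1. In Section 8.3.3.2, state that the response-to-withdrawal condition does not apply to one-off events such as falls, and that having Parkinson's disease or freezing does not by itself lower the grade.
2. In Section 8.3.4, add two AE-form items: device worn at onset, and cue felt at or just before onset (each yes, no or unknown), checked against device logs where available.
3. In Section 9.4.4, tabulate falls by cue-on (21 days) and cue-off (14 days) period per day of device use, so that the fall summary does not rest on the relatedness grade alone.

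A default grade of at least Probably Related for any fall at a cue is not advised. It would replace one artefact with the opposite one and label falls from freezing alone as device-related.

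The sponsor should also reconcile Section 8.3.4 with itself. It says that all adverse events are followed to adequate resolution. It also says that events are monitored until resolution or study completion, with only definitely or probably related ones carried through to resolution or stabilization. This matters here because any change in grading could change which events fall under the last sentence.

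The cost is protocol wording, two form items, slightly longer weekly calls and one table. The on/off comparison is descriptive and confounded with time. It also loses cue-off data from anyone told under Section 6.1.1 to stop wearing the devices in weeks 1 and 5 because remote switching failed.
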